5.6 Benefit-Risk Assessment

The down-regulation of IFN α has been suggested to be possibly beneficial in patients suffering from SLE (Yao *et al.*, 2009b). IFN-K acting as active immunization against IFN α has the capability to induce anti-IFN α antibodies to neutralize IFN α biological activity and therefore has the potential to treat the deleterious effects consequent to over-expression of the cytokine IFN α observed in patients with SLE.

Preclinical data in lupus mice injected with IFN-K, have shown that treatment with IFN-K elicit production of anti-IFN neutralizing antibodies, and significantly reduced progression of the disease, as demonstrated by an increased survival rate, and a reduction in proteinuria. In long term treatment administration in mice models and in repeat toxicity studies in monkeys, IFN-K was well tolerated at the dose, and with the route and the schedule of administration equivalent to the ones proposed in the planned clinical trial (see current version of the IB).

Over the 28 patients enrolled in the previous Phase I-II clinical study, 21 patients with SLE were administered with IFN-K as an intramuscular injection (Lauwerys *et al.*, 2013). IFN-K was generally well tolerated. Few local (including tenderness, swelling, erythema and itching) or systemic reactions were reported, and were mild to moderate in severity and transient in nature. Eight serious adverse events (SAEs) were reported in 5 patients across the whole study (main and extended Follow-up). Two of the SAEs were SUSARs (one flare of underlying lupus occurred for a patient who had received only one injection of IFN-K at 240 μ g and one colon cancer with liver metastasis in a patient who received 4 injections of IFN-K at 120 μ g) (for further details see the current version of the IB).

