In contrast to mab, anti-IFN α antibodies can neutralize all IFN α subtypes and consequently these antibodies should be more effective in reducing the IFN gene signature. Indeed, also in the patients in the Phase I/II who exhibited neutralizing antibodies more than two years after immunization, neutralization of IFN gene signature was still observed (non published data). In addition, significantly higher anti-IFN titers were found in signature-positive patients than in signature-negative patients. In IFN gene signature-positive patients, IFN-K significantly reduced the expression of IFN-induced genes. The decrease in IFN score correlated with the anti-IFN antibody titer. Serum complement C3 levels were significantly increased in patients with high anti-IFN antibody titers (Lauwers *et al.*, 2013).

These results show that IFN-K is well tolerated, immunogenic, and significantly improves disease biomarkers in SLE patients, and are in favor of proceeding with the clinical development.

In the proposed clinical study, treatment with IFN-K or placebo is added in addition to standard therapy, with the exception of potent immunosuppressive agents, such as cyclophosphamide, oral tacrolimus, and cyclosporine A; and biological agents such as rituximab.

The study population will enroll patients with active SLE (SLEDAI \geq 6) and positive IFN gene signature, treated with either CS and/or immunosuppressive drug at screening. In accordance with

the current standard treatments of such patients with active SLE, appropriate guidances are provided in the protocol for the tapering of CS and immunosuppressive drugs along the study, all of this to allow the detection of a significant immunological activity and clinical efficacy of IFN-K while ensuring adequate patients' safety.

In the proposed study, in addition to monitoring of standard safety parameters (ie, physical examination findings, clinical laboratory tests, ECGs, and vital signs), an independent DSMB will oversee the safety of the patients enrolled in the study and monitor the occurrence of flare throughout the study. The iDSMB may recommend stopping the study for safety concerns. Toxicity will be monitored using the Modified World Health Organization (WHO) Toxicity Criteria, which includes graded adverse events on a scale from 0 to 4.

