11.6 SLE Disease Activity Assessment

The specific research instruments that will be used to assess disease activity and quality of life include:

- Chest X-Ray

Chest X-Ray will be obtained where allowed by Local Regulation for SLICC/ACR-DI purpose at Visit 2 (X-Ray obtained within previous month is acceptable) and at Visit 12.

- SLEDAI-2K score (Gladman *et al.*, 2002) - see Appendix 2

The SLEDAI scale measures disease activity. The original version was modified (SLEDAI-2K) to better reflect persistent active disease. There are 24 items in a total of 9 organs/systems; total scores range from 0 (non-active disease) – 105 points. Scores are attributed taking into account disease activity over the previous 10 days.

- BILAG-2004 index (Yee *et al.* 2010) - see Appendix 3

The BILAG 2004 index categorizes disease activity into 5 different levels from A–E, with Grade A representing very active disease and Grade E indicating no current or previous disease activity. Scoring is based on a total of 101 items, grouped into 9 organ/systems. Scores are attributed taking into account the signs/symptoms of SLE occurring over the previous 4 weeks.

- PGA score

PGA score is captured using 100 mm VAS

- SELENA-SLEDAI flare index (Petri *et al.*, 1999; Griffiths, *et al.* 2005) – see Appendix 4

- SLICC/ACR-DI (Gladman *et al.*, 1996) – see Appendix 5

The SLICC/ACR-DI captures permanent changes which have occurred in patients with SLE, regardless of causality. The questionnaire contains 41 items covering 12 different organ systems.

- Count of Tender and Swollen Joints and joint pain VAS – see Appendix 6

Count of Tender and Swollen Joints will be captured with 28-Tender and Swollen Joint counts and Joint pain is captured using 100 mm VAS

- CLASI (Albrecht *et al.*, 2005) – see Appendix 7

The CLASI was specifically developed to assess the cutaneous manifestations of SLE. It measures both disease activity and permanent damage (e.g. dyspigmentation and scarring) over the entire body surface.

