12.1 Definitions

12.1.1 Adverse event

International Conference on Harmonization (ICH) E6 Good Clinical Practice (GCP) Guidelines define an AE as any untoward medical occurrence in a patient or patient administered a pharmaceutical product in a clinical investigation regardless of its causal relationship to the study treatment.

An AE can therefore be any unfavorable and unintended sign (including an abnormal laboratory finding), symptom or disease temporally associated with the use of medicinal (investigational) product, whether or not related to the medicinal (investigational) product. The occurrence of an AE may come to the attention of study personnel during study visits and interviews or by a study recipient presenting for medical care.

All AEs must be graded for intensity and relationship to study product.

SLE flare which is a worsening of the pre-existing SLE condition will be reported as AE.

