13.9.3 Analysis of the Clinical Secondary Endpoints

- The response to treatment according to response criteria described in section 13.3.1 will be analyzed using a logistic regression using the response rate as dependent variable and treatment as independent variable, while adjusting for the minimization factors used for randomization.
- The SRI-4, 6, 8, 10 response to treatment according to response criteria described in section 13.3.1 will be analyzed using a logistic regression using the response rate as dependent variable and treatment as independent variable, while adjusting for the minimization factors used for randomization.
- Number of patients achieving a SLEDAI response, defined as a reduction of the SLEDAI-2K score of at least 4 points at Week 36 compared to baseline will be analyzed using frequency table methods
- BILAG grade changes by body system will be analyzed using non-parametric Wilcoxon-test
- Number of patients with an SLE flare (SELENA-SLEDAI flare index; BILAG flares) will be analyzed using frequency table methods
- Clinical response by assessing disease activity using: SELENA-SLEDAI, SLICC/ACR-DI, and Cutaneous LE Disease Area and Severity Index (CLASI) will be analyzed using a t-test

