4.2.1 Adverse events

Adverse events (AE) will be coded using the MedDRA Version 18 and will be classified by Preferred Term (PT) and System Organ Class (SOC).

A Treatment Emergent Adverse Events (TEAE) will be defined as any adverse event that occurs from the time of first study treatment dose administered to the patient until last study visit.

An SAE is defined as an AE that meets one of the following conditions:

- Death.
- Life threatening event (defined as any AE that places the patient, in the view of the Investigator, at immediate risk of death from the event as it occurred, i.e., it does not include an event that had occurred in a more severe form, might have caused death).
- An event requiring inpatient hospitalization or prolongation of existing hospitalization during the period of protocol defined surveillance.
- Results in a persistent or significant disability/incapacity.
- Congenital anomaly or birth defect in the offspring of a study participant.
- Any other important medical event that may not result in death, be life threatening, or require hospitalization, may be considered a serious adverse experience when, based upon appropriate

Statistical Analysis Plan

Study Name: IFN-K-002

SAP version & date: v4, 18/Jun/2018

medical judgment, the event may jeopardize the patient and may require medical or surgical intervention to prevent one of the outcomes listed above. Examples of such medical events include allergic bronchospasm requiring intensive treatment in an emergency room or at home, blood dyscrasias or convulsions that do not result in inpatient hospitalization, or the development of drug dependency or drug abuse.

Tolerability/safety will be assessed over the 36 weeks study period. The analysis will focus on:

- Occurrence and intensity of any solicited local and systemic reactions during a 7-day follow-up period (i.e. day of study product administration and 6 subsequent days) after each IFN-K or placebo dose
- Occurrence, intensity and relationship of unsolicited AEs occurring throughout the study period
- Occurrence, intensity and relationship of all SAEs occurring throughout the study period
- Rate and severity of viral infections
- Flares (time of occurrence in relation to product administration)

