SAP version & date: v4, 18/Jun/2018

The BILAG global score will be defined as the summation of the numerical values for the nine-system scores as given by the following formula:

$$\text{Numerical global score (xs)} = A*12 + B*8 + C*1$$

Where A, B and C represent the number of Grades A, B and C respectively at each assessment. Grades D and E are considered as 0 (Chee-Seng Yee *et al*, 2010).

All BILAG data will be listed in Listing 16.2.6.3.

5.2.4.3.4 *SELENA SLEDAI flare index*

The numbers of patients with a mild or moderate, or severe SLE flare (SELENA-SLEDAI flare index) and corresponding number of SLE flare will be presented. (Statistical table 14.2.13).

The total score at each visit (planned in the protocol) and change from baseline by treatment group will also be presented. The change at Week 36 will be analyzed using a t-test. (Statistical tables 14.2.14.1 to 14.2.14.2).

All SELENA-SLEDAI flare index data will be listed in Listing 16.2.6.4.

5.2.4.3.5 *SLICC/ACR-DI*

Total score at each visit and change from baseline by treatment group will be presented. The change at Week 36 will be analyzed using a t-test. (Statistical tables 14.2.15.1 to 14.2.15.2).

All SLICC/ACR-DI data will be listed in Listing 16.2.6.5.

5.2.4.3.6 *CLASI*

Total activity score and Total damage score at each visit and change from baseline by treatment group will also be presented. The changes at Week 36 will be analyzed using a t-test. (Statistical tables 14.2.16.1 to 14.2.17.2).

All CLASI data will be listed in Listing 16.2.6.6.

5.2.4.3.7 *LLDAS*

Number of patients achieving a LLDAS at Week 36 will be presented by treatment group (Statistical table 14.2.18). It is defined as:

- SLEDAI-2K ≤ 4 , with no activity in major organ systems (renal, CNS, cardiopulmonary, vasculitis, fever) and no haemolytic anaemia or gastrointestinal activity
- No new features of lupus disease activity compared with the previous assessment (New feature is defined as any BILAG item recorded as "new" (modality 4) at Week 36)
- Physician global assessment (PGA, scale 0–3) ≤ 1
- Current prednisolone (or equivalent) dose ≤ 7.5 mg daily (this criterion will be identified by medical review)
- Well tolerated standard maintenance doses of immunosuppressive drugs and approved biological agents, excluding investigational drugs (this criterion will be identified by medical review)

Statistical Analysis Plan

Study Name: IFN-K-002

SAP version & date: v4, 18/Jun/2018

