7.5 LLDAS

Analysis for LLDAS, initially not planned in the protocol, will be done.

8 Software documentation

All summaries and statistical analyses will be generated using SAS version 9.4 or higher.

Statistical Analysis Plan

Study Name: IFN-K-002

SAP version & date: v4, 18/Jun/2018

9 Derived data

Derived variable	Derivation algorithm
Change from baseline to visit V (continuous)	
Change from baseline of variable X=X(Visit V)-X(Baseline)
 
 ○ Negative values indicate a decrease in X ○ Positive values indicate an increase in X
Percent change from baseline to visit V (continuous)	
Percent change from baseline of variable X=100 *[X(Visit V)-X(Baseline)]/X(Baseline)
 
 ○ Negative values indicate a decrease in X ○ Positive values indicate an increase in X
Treatment Compliance (continuous)	
The compliance Ci for patient i will be computed according to:
 $C_i = \frac{D_i^t * 100}{D_i^p}$ 
where D_i^p mg is the total amount (mg) of IP prescribed to patient i and D_i^t is the total amount (mg) of IP actually taken by the patient during the study i.e., before the end of study for patient i.

Treatment compliance (categorical) (if relevant)	
Categorial variable with three modalities:
 
 • $C_i < 80\%$ • $80\% \leq C_i < 120\%$ • $C_i \geq 120\%$
Event Duration	$(\text{End Date}) - (\text{Start Date}) + 1$
BILAG score	See BILAG-2004 Index scoring
SLEDAI-2K and SELENA SLEDAI	Sum of the weights
SLICC/ACR	Sum of items
CLASI	Sum of items
FACIT	See FACIT-Fatigue Subscale Scoring Guidelines (Version 4)

Statistical Analysis Plan

Study Name: IFN-K-002

SAP version & date: v4, 18/Jun/2018

Derived variable	Derivation algorithm
SF-36	See SF-36 Health Survey, Manual and Interpretation Guide
Time to event SLE flare	
SLE flare will be identified in BILAG-2004 scoring.
 
SLE flares are predefined as a BILAG A or B score due to items that were new or worse in any of the eight organ system (Isenberg et Al).
 
For patient with a SLE flare: Time to event = Visit date of corresponding BILAG – Date of Week 0 + 1
 
For patient without SLE flare: Time to event = Date of Week 36 (or date of end of study for patients prematurely withdrawn before Week 36) – Date of Week 0 +1

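### The SAP keeps BILAG flares as a secondary endpoint but plans no count of them by arm, and its flare rule covers eight systems of a nine-system index

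*SAP*

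**What the plan says.** Protocol 13.9.3, on the clinical secondary endpoints, states: "Number of patients with an SLE flare (SELENA-SLEDAI flare index; BILAG flares) will be analyzed using frequency table methods". SAP 4.1.2.1 retains flare incidence on both instruments as a secondary endpoint.

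The analysis in SAP 5.2.4.3.4 covers one instrument: "The numbers of patients with a mild or moderate, or severe SLE flare (SELENA-SLEDAI flare index) and corresponding number of SLE flare", reported in Table 14.2.13. SAP 5.2.4.3.3, on BILAG, gives shift tables and a global score but no flare count. SAP 5.2.4.5.2 analyses time to first flare by Cox regression, once with treatment group and once within IFN-K patients by neutralizing-antibody status.

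SAP Section 9 takes those flares from BILAG-2004 scoring: an A or B score arising from items that were "new or worse in any of the eight organ system". Protocol 11.6 describes the same index differently: "Scoring is based on a total of 101 items, grouped into 9 organ/systems". SAP 5.2.4.3.3 also sums nine systems for the global score.

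Flare is a safety matter in both documents. Protocol 5.6 reports two SUSARs in the earlier study, of which "one flare of underlying lupus occurred for a patient who had received only one injection of IFN-K" is one, and gives the iDSMB the task to "monitor the occurrence of flare throughout the study". SAP 4.2.1 lists among its safety focuses "Flares (time of occurrence in relation to product administration". Protocol 12.1.1 adds: "SLE flare which is a worsening of the pre-existing SLE condition will be reported as AE".

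**The concern.** A secondary analysis required by the protocol has no output in the SAP, and SAP Section 7, which lists departures from the protocol, is silent about it. The dedicated flare count that remains rests on the instrument with fewer scheduled visits. The instrument scored every four weeks, whose scores are validated by a blinded adjudication committee (Protocol 10.2.1 and 10.5), is used only for the time to the first event.

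The eight-system rule leaves one system out without naming it. A programmer would have to guess which, and the guess changes the events in the Cox models.

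At stake is a direct, by-arm statement of how many patients had a BILAG flare, how many flares there were, and when they occurred. The earlier SUSAR followed a single injection, so early flares deserve a table of their own.

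**Working it through.** The plan states no flare rate, so there is no figure to reproduce. The check traces each flare item through the documents and then compares the assessment schedules.

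**1. From protocol to output**

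| Item | Protocol | SAP endpoint | SAP analysis | SAP table |
|---|---|---|---|---|
| SELENA-SLEDAI flares | 13.9.3 | 4.1.2.1 | 5.2.4.3.4 | 14.2.13 |
| BILAG flares, number of patients | 13.9.3 | 4.1.2.1 | none | none |
| Number of SLE flares (instrument not stated) | 13.9.6 | 4.1.3 | SELENA-SLEDAI count only | 14.2.13 |
| Time to first flare | 13.9.6, life-table | 4.1.3 | 5.2.4.5.2, Cox, BILAG-defined | 14.2.29.1, 14.2.29.2 |
| Flare timing relative to dosing | none | 4.2.1 | none specific to flare | general TEAE tables 14.3.7.1 to 14.3.7.6 |

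SAP Section 7 covers the relabelled population, the added mixed model, composite SRI-4, the dropped lupus-therapy analysis, the one-hour reactions, laboratory change and LLDAS. Nothing in it concerns flares.

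**2. Scheduled post-baseline assessments** (Protocol Table 1 and 10.9)

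- SELENA-SLEDAI flare index: Weeks 24 and 36. That is 1 by Week 24 and 2 by Week 36. It is also on the early termination list (Protocol 10.9.13).
- BILAG-2004: Weeks 4, 8, 12, 16, 20, 24, 28, 32 and 36. That is 6 by Week 24 and 9 by Week 36.

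**3. Calendar coverage**

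Coverage = (visits × look-back in days) / days in the window. The look-backs do not overlap; visit windows and early termination visits are ignored. Weeks 0–24 are 168 days and Weeks 0–36 are 252 days.

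- BILAG, 4-week look-back (Protocol 11.6): 6 × 28 / 168 = 100%; 9 × 28 / 252 = 100%.
- SELENA-SLEDAI, if the 10-day look-back stated for the score descriptors (Protocol Appendix 4) held for the whole form: 1 × 10 / 168 = 6.0%; 2 × 10 / 252 = 7.9%.
- SELENA-SLEDAI, with an assumed 28 days: 28 / 168 = 16.7%; 56 / 252 = 22.2%.
- SELENA-SLEDAI, if the other flare items are read as since the last form: 168 / 168 = 100%; (168 + 84) / 252 = 100%.

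The documents do not say which reading applies to the items outside the score (new or worse manifestations, treatment changes, hospitalization, physician global). Coverage therefore lies anywhere from 7.9% to 100% of the main study. It is a share of days, not of flares.

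**4. Systems**

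The index has nine and the flare rule has eight: 9 − 8 = 1 system, unnamed, whose flares would not be events in either Cox model.

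**5. Dose timing**

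Doses are given at Weeks 0, 1, 4, 12 and 24. The first post-baseline BILAG is at Week 4, the visit of dose 3, and looks back over four weeks that contain doses 1 and 2. BILAG therefore cannot separate the dose 1 interval from the dose 2 interval. Adverse-event onset dates can.

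**The case against.** The strongest reply is that flares are far from ignored, and much of it stands.

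- Table 14.2.29.1 compares the arms on time to first BILAG flare from four-weekly scores, and such an analysis can respond to an early excess.
- Reporting flares as adverse events is an instruction, not an option. TEAEs are tabulated by preferred term, arm and dose period, and the listings carry onset date and period.
- The SELENA-SLEDAI form is also completed at early termination where possible, so some patients who leave before Week 24 will have one.
- In-trial flare monitoring belongs to the iDSMB under its own charter and does not depend on this SAP.

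A reader might infer that most flares in the dosing window go uncounted, or that the trial could not say after which dose flares occurred. The documents support neither. They give no flare rate or duration, the 10-day look-back attaches only to the score descriptors, and the adverse-event tables run by dose period.

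The reply does not remove the gap. A Cox model stops at the first flare, and the SAP asks for no count by arm beside it. The by-period TEAE tables have no defined grouping of terms for flare, so no flare total is specified. Neither output replaces the BILAG frequency table that the protocol requires, and neither resolves eight against nine systems.

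**Conclusion.** The point holds in a limited form. One analysis of a component of a secondary endpoint, BILAG flares by arm, is missing from the SAP and the omission is undeclared. The dedicated flare count uses an instrument with 2 scheduled post-baseline visits against 9 for BILAG. The BILAG flare rule omits one unnamed system of nine. The flare timing promised in SAP 4.2.1 has no output of its own.

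Early, repeat or ninth-system flares may therefore be absent from the dedicated flare analyses. Their share cannot be computed from the documents, and the coverage range above should not be read as one. The conclusion rests on the SAP's analysis sections and table list being complete as written. The co-primary analyses are not affected.

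**What to change.** 1. Restore the protocol's table: number and percentage of patients with at least one BILAG flare, and number of flares, by arm, on the FAS, for Weeks 0–36 and for visit-based intervals (Weeks 0–4, 4–12, 12–24, 24–36). These hold 1, 2, 3 and 3 of the nine BILAG visits.
2. In SAP Section 9, apply the flare definition to all nine BILAG-2004 systems, or name the excluded system and justify it. The SAP takes its rule from a cited publication not available here, so either course is open. Use the same definition in the new table and in both Cox models.
3. For timing by dose, including dose 1 against dose 2, tabulate flares reported as adverse events by arm and dose period, using onset dates and a group of preferred terms fixed before unblinding.
4. State the look-back of the SELENA-SLEDAI flare items outside the score.
5. Record these changes, and the move from life-table methods to Cox regression, in SAP Section 7.

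The cost is two tables, one definition, one clarification and a Section 7 entry. All the data are already collected, so no new procedure or visit is needed.

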5.2.4.3 Secondary efficacy analyses

Secondary efficacy analyses will be performed on the FAS population except if otherwise specified.

5.2.4.3.1 *SRI response*

The SRI-4, 6, 8, 10 responses will be described at Week 36. (Statistical tables 14.2.5.1, 14.2.5.4, 14.2.6.1, 14.2.7.1, 14.2.8.1)

The SRI-4 response (section 4.1.2.1) will be analyzed using the same method as the primary analysis for the second co-primary endpoint (logistic regression). This analysis will be performed both on the FAS and PP sets. (Statistical tables 14.2.5.2 & 14.2.5.5)

The model on FAS for patients IFN-K treated with the status of IFN α neutralizing antibodies (positive/negative) at Week 36 as dependent variable will be also presented (Statistical table 14.2.5.3).

The SRI-6, 8, 10 responses to treatment at week 36 will also be analyzed using a logistic regression using the response rate as dependent variable and treatment as independent variable, while adjusting for the minimization factors used for randomization. (Statistical tables 14.2.6.2, 14.2.7.2, 14.2.8.2)

All analyses performed on SRI-4 will also be conducted on the composite SRI-4 (both with tapering CS \leq 5 mg and \leq 7.5 mg) on the FAS population only. (Statistical tables 14.2.5.6 to 14.2.5.11)

The SRI-4 response is an important and alternative endpoint assessing the clinical response. In case, there will be no trend on the BICLA response, the SRI-4 response could be chosen as primary endpoint for further development of IFN-K.

5.2.4.3.2 *SLEDAI response*

Number of patients achieving a SLEDAI response, defined as a reduction of the SLEDAI-2K score of at least 4 points at Week 36 compared to baseline will be analyzed using frequency table methods (Statistical table 14.2.9).

SLEDAI-2K score at each visit and change from baseline by treatment group will also be presented (Statistical tables 14.2.10.1 to 14.2.10.2).

All SLEDAI data will be listed in Listing 16.2.6.2.

5.2.4.3.3 *BILAG*

Shift tables between Baseline and LVA (last available value between Week 36 and Week 24) will also be presented for each body system. (Statistical table 14.2.11)

Finally, descriptive statistics for the BILAG global score at each visit and change from baseline to LVA will be presented. The difference between treatment groups for the change from baseline to LVA will be analyzed using the non-parametric Wilcoxon-test. (Statistical table 14.2.12)

Statistical Analysis Plan

Study Name: IFN-K-002

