5.2.4.5 Exploratory analyses

The following analysis will be performed on the FAS population except if otherwise specified.

5.2.4.5.1 **PGA scores**

PGA score at each visit and change from baseline by treatment group will be presented. (Statistical tables 14.2.28.1 to 14.2.28.2)

All PGA data will be listed in Listing 16.2.6.10.

5.2.4.5.2 **SLE flares**

Time to first SLE flare in patients will be analyzed using a cox regression model.

The first model will be adjusted on treatment group.

The second model will be performed only on patients IFN-K treated and will be adjusted on presence/absence of neutralizing antibodies. (Statistical tables 14.2.29.1 to 14.2.29.2)

5.2.4.5.3 **28-Tender and Swollen Joint Counts (SJC)**

28-Tender and Swollen Joint Counts and Joint Pain VAS at each visit and change from baseline will be presented. The changes at Week 36 will be analyzed using a t-test. (Statistical tables 14.2.30.1 to 14.2.32.2).

28-Tender and Swollen joint counts data will be listed in Listing 16.2.6.11, and joint Pain VAS data in Listing 16.2.6.12.

5.2.4.5.4 **Treatment failure**

- Proportion of treatment failure will be analyzed using frequency table methods. Patients will be considered as treatment failure if they receive more than 5 mg prednisone equivalent/day at any time between Week 24 (Visit 9) and Week 36 (Visit 12) or if their CS dose is increased above the Week 24 level is recorded (this criterion will be identified by medical review) (Statistical table 14.2.33)

5.2.4.5.5 **SF-36**

Statistical Analysis Plan

Study Name: IFN-K-002

SAP version & date: v4, 18/Jun/2018

Physical Component Summary (PCS) and Mental Component Summary (MCS) scores at each visit and change from baseline will be presented. The changes at Week 36 will be analyzed using a non-parametric Wilcoxon rank sum test (Statistical tables 14.2.34.1 to 14.2.35.2). If one is statistically significant then the individual domain scores will also be described.

In addition, number of patients with clinically meaningful improvements \geq Minimum Clinically Important Differences (MCID) of 2.5 points for summary and 5.0 points for domain scores between baseline and Week 36 will be presented. (Statistical tables 14.2.36 to 14.2.37)

All SF-36 data will be presented in Listing 16.2.6.13.

5.2.4.5.6 **FACIT**

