5.3 Statistical/Analytical issues

5.3.1 Adjustments for Covariates

All models ANCOVA, MMRM, Logistic regression) will be adjusted on the minimization factors used for randomization (Ethnic (see section 9 Derived data) Origin, Age group, Presence or absence of renal involvement according to the BILAG at screening, With or without CS treatment at screening, With or without HCQ treatment at screening, With or without MMF treatment at screening).

In addition, MMRM will be adjusted on the baseline value.

For “Ethnic origin”, the reclassified values (see section 9 Derived data) will be used for primary analysis. The values from the eCRF will be used for sensitivity analysis. In the same way, for “Presence or absence of renal BILAG at screening”, the re-computed renal BILAG score derived in the statistics analysis datasets will

Statistical Analysis Plan

Study Name: IFN-K-002

SAP version & date: v4, 18/Jun/2018

be used for primary analysis. The values from the eCRF will be used as sensitivity analysis. (Statistical tables 14.2.3.1.4 & 14.2.3.2.3)

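### Eight clinical scales are compared by unadjusted t-tests on Week 36 change, giving up precision that the Week 0 score and the minimisation factors could supply

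*SAP*

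**What the plan says.** SAP 5.2.4.3.4 (SELENA-SLEDAI score) and 5.2.4.3.5 (SLICC/ACR-DI) plan the same comparison: "The change at Week 36 will be analyzed using a t-test". SAP 5.2.4.5.6 does so for FACIT. SAP 5.2.4.3.6 (CLASI activity and damage) and 5.2.4.5.3 (tender count, swollen count, joint-pain VAS) use the plural: "The changes at Week 36 will be analyzed using a t-test". None of these sections names a covariate.

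The protocol agrees. Section 13.9.3 states "Clinical response by assessing disease activity using: SELENA-SLEDAI, SLICC/ACR-DI, and Cutaneous LE Disease Area and Severity Index (CLASI) will be analyzed using a t-test", and 13.9.6 plans t-tests for the joint measures and FACIT.

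SAP section 9 defines change as the visit value minus the baseline value. SAP 5.3.1 says that the ANCOVA, MMRM and logistic models "will be adjusted on the minimization factors used for randomization" and adds the baseline value to the MMRM only. The t-tests fall under neither rule. All eight scales are scheduled at Week 0 and Week 36 (Protocol Table 1).

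Other continuous clinical scores are handled differently. For the BILAG global score, "The difference between treatment groups for the change from baseline to LVA will be analyzed using the non-parametric Wilcoxon-test". For SF-36 PCS and MCS, "The changes at Week 36 will be analyzed using a non-parametric Wilcoxon rank sum test". Two scores are only described: "SLEDAI-2K score at each visit and change from baseline by treatment group will also be presented", and "PGA score at each visit and change from baseline by treatment group will be presented".

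**The concern.** Two sources of precision are left unused.

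- **Baseline.** Subtracting the Week 0 score fixes its coefficient at 1. An ANCOVA estimates that coefficient. The change-score variance exceeds the ANCOVA variance by the baseline variance times (1 − slope)², so in large samples ANCOVA is more precise unless the slope is exactly 1. None of the eight scales is a minimisation factor, so allocation does not directly control chance imbalance on them. Patients are also selected for active disease (Protocol 8.3.1), so regression to the mean is plausible for the activity scales. A change score then over-corrects any imbalance.
- **Minimisation factors.** Allocation balances six factors (Protocol 9.2.2). If they predict the outcome, balancing them removes their contribution from the treatment difference. An unadjusted t-test still counts that contribution in its standard error and is therefore conservative. The SAP uses the factors for both co-primaries and for SRI-4, 6, 8 and 10, but not here.

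At stake is the chance of seeing real effects on disease activity, joints, pain and fatigue in a phase IIb trial sized at 80 evaluable patients per arm.

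**Working it through.** **Inputs from the documents.** 80 evaluable patients per arm, two-sided 5% (Protocol 13.1, SAP 5.1.2). Six minimisation factors: ethnic origin with four categories (3 parameters) plus five two-level factors, giving 3 + 5 = 8 parameters.

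**Inputs assumed.** The correlation r between Week 0 and Week 36, and equal SDs at both times. The documents give no SD, correlation or power for these scales.

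**Step 1: the plan's own figure.** The only t-test power stated is for the first co-primary: 85% for a difference of 32.6 with SD 68. The standardised difference is 32.6 / (68 × √(2/80)) = 3.03. The normal approximation gives 85.8% and the noncentral t with 158 df gives 85.4%, so the plan's figure reproduces.

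**Step 2: effect of the baseline covariate.** With common SD s:

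- Variance of change = 2s²(1 − r)
- Residual variance under ANCOVA = s²(1 − r²)
- Ratio of standard errors = √((1 + r)/2)

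**Step 3: cost of estimating covariates.** With N = 160 and p covariate parameters, the width is multiplied by √((N − 3)/(N − 3 − p)) and by a ratio of t quantiles very close to 1. For p = 1 (baseline) the first term is √(157/156) = 1.003. For p = 9 (baseline plus eight) it is √(157/148) = 1.030. The eight parameters alone therefore cost about 2.5 to 3%.

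At r = 0.5, √0.75 = 0.866. Then 0.866 × 1.003 = 0.869 and 0.866 × 1.030 = 0.892. If the factors explain 10% of residual variance, 0.892 × √0.90 = 0.847.

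**Step 4: 95% CI width relative to the planned t-test.**

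| r | Baseline only | Baseline + factors explaining nothing | Baseline + factors explaining 10% |
|---|---|---|---|
| 0.3 | 0.809 | 0.831 | 0.788 |
| 0.5 | 0.869 | 0.892 | 0.847 |
| 0.7 | 0.925 | 0.950 | 0.901 |
| 0.9 | 0.978 | 1.004 | 0.953 |
| 0.95 | 0.991 | 1.017 | 0.965 |

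A simulation of 3,000 trials per value of r gave 0.809, 0.869, 0.925 and 0.977 for baseline only at r = 0.3, 0.5, 0.7 and 0.9. With eight uninformative factors added it gave 0.830, 0.892, 0.950 and 1.003.

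**Step 5: in power terms.** Take an effect that the t-test detects with 60% power. At r = 0.5, baseline alone gives (1.960 + 0.253)/0.866 − 1.960 = 0.60, or about 72%. With eight uninformative factors, 2.213/0.892 − 1.960 = 0.52, or about 70%.

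**Step 6: dependence on equal SDs.** Let k be the Week 0 SD divided by the Week 36 SD. The variance ratio becomes (1 − r²)/(1 + k² − 2kr). At r = 0.5 it is 0.75 for k = 1, 0.75/0.79 = 0.95 for k = 0.7, and 0.75/1.56 = 0.48 for k = 1.4. The gain could be much smaller or larger than the table shows.

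**The case against.** A t-test on change is a valid comparison in a randomised trial, and the SAP follows the protocol in using it. None of these endpoints enters the sequential test (SAP 5.3.5) or the success rule (SAP 5.2.4.1). The gain cannot be quantified from the documents. All of that stands, and it limits the weight of the point.

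Four stronger readings are tempting, and the documents do not support them.

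- **That all continuous clinical endpoints are treated this way.** BILAG global score and SF-36 have Wilcoxon tests, and SLEDAI-2K and PGA scores have no between-arm test.
- **That the baseline score is ignored.** It is subtracted; what is missing is its use as a covariate.
- **That every scale would gain at no cost.** Protocol 11.6 describes SLICC/ACR-DI as recording permanent change and CLASI as covering permanent damage as well as activity. Their correlation over 36 weeks is probably high (an inference), and at r of 0.9 or more the full model gains nothing unless the factors are prognostic. The secondary objective also limits CLASI to patients with skin lesions at baseline. If that limit is applied, covariates cost more: with 40 per arm, assumed for illustration, nine parameters multiply the width by √(77/68) = 1.06.
- **That the t-tests are always conservative.** That holds only if the minimisation factors predict the outcome.

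Joint counts and damage indices are also bounded counts or sums, so a linear model needs checking. The planned t-test already treats them as numerical scores, so this does not favour leaving the plan as it is.

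**Conclusion.** The point holds as an efficiency improvement for the eight named scales. Nothing elsewhere in the SAP or protocol supplies the missing adjustment. A reader might infer bias or a false-positive risk, but neither follows: the tests are valid, type I error is not inflated and the co-primaries are not affected.

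Under equal SDs, the baseline covariate alone narrows the CI by about 19%, 13%, 7% and 2% at r = 0.3, 0.5, 0.7 and 0.9. The full model, if the factors are uninformative, narrows it by about 17%, 11% and 5% at the first three values, is neutral at 0.9 and about 2% wider at 0.95. The benefit therefore lies mainly with the activity, joint, pain and fatigue scales, while SLICC/ACR-DI and CLASI damage may gain nothing. These sizes rest on assumed values of r and on equal SDs.

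**What to change.** In SAP 5.2.4.3.4 to 5.2.4.3.6, 5.2.4.5.3 and 5.2.4.5.6, replace each t-test with an ANCOVA of the Week 36 value on treatment, the Week 0 value of the same scale and the six minimisation factors of SAP 5.3.1. Using change as the outcome gives the same treatment estimate once baseline is in the model. Extend the baseline sentence in SAP 5.3.1 to these models, record the departure from Protocol 13.9.3 and 13.9.6 in SAP section 7.2.2, and keep the descriptive tables of change.

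The cost is SAP wording before database lock and a modified version of the planned ANCOVA program. The co-primary program cannot be reused unchanged, because its outcome is percent change and it has no baseline covariate (SAP 5.2.4.1). For scales with very high r, up to about 3% of CI width could be lost at 80 per arm. No new data, visits or patients are needed.
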